**Table 1. Events for subjects in GROUPS I and III:**

Visit	Visit 1	Visit 2
Assessments	Screening	MRI Study 1
Schedule	DAY -30 to -7	Day 0-30
Routine Blood Chemistries, CBC, UA, lipid profile, TSH/ T4, A1c, NT-proBNP, hCG	X	
ECG, DXA, ECHO (if not done within 3-6 months of screening)	X	
Vital signs	X	X
Baseline Cardiac MRI and baseline blood samples $\times$ 3: $\beta$ -OH-butyrate, acetoacetate, glucose, FFA, lactate, pyruvate, glycerol, HCO 3 , insulin/C-pep, glucagon, renin and aldosterone		X
Blood safety monitoring before (3 samples) and after (3 samples) the infusion: glucose, potassium with iSTAT		X
Prime-continuous infusion of $\beta$ -OH-B (0.8 M solution; pH adjusted to 7.24) to increase the plasma $\beta$ -OH-B concentration by GROUP I: ~0.5 mmol/L (6-hrs) GROUP III: ~5.0 mmol/L (3-hrs)		X
Post-infusion Cardiac MRI and blood samples $\times$ 3: NT-proBNP, $\beta$ -OH-butyrate, acetoacetate, glucose, FFA, lactate, pyruvate, glycerol, HCO 3 , insulin/C-pep, glucagon, renin and aldosterone		X

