**Subjects:** 78 type 2 diabetic subjects with New York Heart Association (NYHA) Class II-III heart failure (75) and ejection fraction less than 45% (documented by patient's medical records with an ECHO or any other heart imaging study) will be studied. Other inclusion criteria include age = 18-80 years; BMI =23-38 kg/m^2; approximately 39 males/39 females; HbA1c = 5.5.0-10.0%; BP < 145/85 mmHg; eGFR > 30 ml/min•1.73 m^2. Subjects must be on a stable dose of guideline-directed heart fail medication (i.e. ACEI, ARB, ARNI, beta blocker, diuretic and/or mineralocorticoid receptor antagonist). Patients must be on stable antihypertensive therapy for at least 2 months. Only diabetic subjects treated with diet/exercise, metformin monotherapy, sulfonylurea monotherapy, low-dose (defined as  $\leq$  45 IU total daily dose) insulin therapy or combination metformin/SU/low-dose insulin therapy. Diabetic subjects treated with a GLP-1 RA or DPP4i (since they inhibit glucagon secretion) or pioglitazone (since it improves skeletal muscle and myocardial insulin sensitivity), SGLT2 inhibitor (since they increase plasma ketone concentration) or high-dose insulin will be excluded. Only subjects whose body weight has been stable ( $\pm$ 4 pounds) over the last 3 months will be studied. Subjects with contraindications for MRI procedures will be excluded, including patients with pacemakers. Women who are pregnant or breastfeeding will be excluded. All subjects with NY Heart Association Class II-III will be recruited from the Heart Failure Clinic at the University of Texas Health Science Center ([name] and [name]). Medical records for Cardiology and Diabetes clinics will be reviewed for eligibility and if potential participants meet inclusion/exclusion criteria they will be contacted about participating in the study. Collectively, these two clinics follow  $\sim$ 4,700 patients who have NYHA Class II-III and approximately 40% of these individuals have type 2 diabetes mellitus. The study will be approved by the UTHSCSA IRB and all subjects will provide written voluntary consent prior to participation.

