**Study Protocol:** Up to 100 Study participants will be asked to fast prior to consenting to the study and the day of the screening visit (day -30 to -7) participants will first sign consent form and eligibility criteria (A1c, eGFR, BP etc) will be confirmed and subjects will undergo a medical history and physical exam to exclude major organ system diseases other than diabetes and cardiac disease. Routine blood chemistries, CBC, urinalysis, lipid profile, TSH/T4, NT-proBNP, and EKG will be obtained. Blood pressure will be measured after reclining for 5 minutes in a quiet room and the mean of three measurements will be recorded. Subjects also will have a DEXA to measure total body fat content. If patient has not had an ECHO within 3-6 months of the screening visit, we will refer patient to the cardiac ECHO to confirm that the EF is < 50% (76).

Within 1-4 weeks after the screening visit, subjects will return to the Research Institute (RI) at 0700 h for a cardiac MRI (19,77) to confirm that the EF is < 50% and to obtain quantitative measures of baseline cardiac functional parameters: chamber volumes and pressures, wall thickness, LV diastolic function (E/A ratio, peak LV filling rate, diastolic volume) and LV systolic function (cardiac output, stroke volume, systolic volume, peak LV ejection rate). Strain and tagging also will be measured. To reduce the likelihood of hypoglycemia during the study procedures, subjects will be asked to withhold their antidiabetic therapy on the day of the studies until they have received a meal at the end of the study days.

Cardiac MRI will be performed by [name]. (Professor, Department of Radiology, UTHSCSA) on 3.0T MRI System (TIM, Trio, Siemens Medical Solution, Malvern, PA) with six channel anterior phased-array torso coil and corresponding coil elements (12 channels total) (19,77). Before cardiac MRI, catheters will be inserted into both antecubital veins for all blood withdrawal and  $\beta$ -OH-B infusion, respectively. Three blood samples will be drawn at 10-15 minute intervals for measurement of NT-proBNP, -OH-butyrate, acetoacetate,

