glucose, FFA, lactate, pyruvate, glycerol, HCO3, insulin, glucagon, renin and aldosterone. Axial and sagittal localizer views, standard two-, three-, and four-chamber views, with 7 mm thick slices are obtained using gradient echo sequence (2.2 x 1.3 mm^2 pixel). Cine imaging with retrospective gaiting is used with a balanced steady-state free precision sequence (TR/TE = 2.44/1.22 ms). Acquisitions consist of 25-30 cardiac phases, matrix 224 x 288, FOV 336 x 430 mm^2, 1.5 x 1.5 mm^2 pixel area. Contiguous short-axis slices are acquired during repetitive breath-holds at expiration. Mitral inflow images are obtained using phase-contrast gradient-echo (PCGE) sequence with through-plane velocity encoding (Venc = 100 cm/s) at the mitral valve with flip angle = 10° and TR/TE = 5.8/3.6 ms. PCGE slice thickness was 8 mm with typical FOV = 228 x 430 mm^2, matrix = 192 x 102, producing 2.89 x 2.89 x 8.0 mm pixel volumes.

Following completion of the baseline MRI, subjects will be divided into three groups (19 subjects per group). Each group will receive a 6-hour (3-hour in group III) prime-continuous infusion of racemic  $\beta$ -OH-B (100 mg/mL solution; pH adjusted to 7.4) to increase the plasma  $\beta$ -OH-B concentration by ~0.5, ~2.0, and ~5.0 mmol/L (43,74).

GROUP I: Prime = 0.4 mg/kg.min for 20 minutes and constant rate = 0.2 mg/kg.min until study end

GROUP II: Prime = 1.5 mg/kg.min for 20 minutes and constant rate = 0.75 mg/kg.min until study end

GROUP III: Prime = 4.0 mg/kg.min for 20 minutes and constant rate = 2.0 mg/kg.min until study end

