These 3 infusion rates were chosen to cover the range of observed increments in plasma ketone concentrations in type 2 diabetic patients treated with a SGLT2 inhibitor: a  $\beta$ -OH-B increment of ~0.5 mmol/L typically is seen in diabetic individuals treated with an SGLT2 inhibitor, while a  $\beta$ -OH-B increment of 2-5 mmol/L is observed in ~5-10% of individuals (54-62). After 5 (or 2) hours of  $\beta$ -OH-B infusion, the cardiac MRI will be repeated. All baseline blood samples will be repeated at 360, 365, and 370 minutes (6 hours) or at 180, 185, and 190 minutes (3 hours) after the start of the  $\beta$ -OH-B infusion. Based upon prior studies from our group (42), we expect to reach steady state levels of  $\beta$ -OH-B in 60 minutes; this will be documented by measuring  $\beta$ -OH-B (and acetoacetate) levels every 30-60 minutes throughout the study. From the study of Gormesen et al (70), we know that 6 hours is sufficient to see a significant reduction (by 50%) in myocardial glucose uptake in normal-glucose-tolerant subjects. Blood glucose and electrolytes are monitored throughout the study with the instantaneous-result device (iSTAT Handheld Analyzer), and potassium supplement may be given before the start of the  $\beta$ -OH-B infusion to prevent decrease in blood potassium level. The investigator will decide to give 20-40mEq of KCL to subjects with initial potassium in the low limit of normal. The investigator will make this decision based on the risk of the subject to develop low serum potassium based on their medical history and renal function. The contraindication for KCL supplementation is elevated blood potassium. It is unlikely that diabetic patients w not taking an insulin secretagogue (i.e. sulfonylureas) will develop hypoglycemia.

Therefore, individuals with history of taking insulin secretagogues (i.e. sulfonylureas) will have hourly glucose monitoring during the  $\beta$ -OH-B infusion to ensure early detection of hypoglycemia. If at any time a subject develops any symptoms suggestive of hypoglycemia (i.e. anxiety, diaphoresis, hunger, weakness etc.) glucose will be measured immediately. If hypoglycemia occurs, we will treat subjects with 15 grams of rapid acting carbohydrates (i.e. juice), and re-check subject's blood glucose level in 15 minutes, and repeat if necessary, until normoglycemia has been reached.

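### The hourly glucose rule covers only subjects with a sulfonylurea history; eligible insulin users without one have no stated checking interval during MRI-day infusions

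*Combined protocol and SAP*

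**What the plan says.** **Eligibility.** The Subjects paragraph of Experimental Design admits patients on low-dose insulin, with the limit and permitted combinations given as "45 IU total daily dose) insulin therapy or combination metformin/SU/low-dose insulin therapy". Higher insulin doses are excluded.

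**The hourly rule.** The Study Protocol section first states its premise, that hypoglycaemia is unlikely in diabetic patients "not taking an insulin secretagogue (i.e. sulfonylureas) will develop hypoglycemia". From this it derives the rule: "individuals with history of taking insulin secretagogues (i.e. sulfonylureas) will have hourly glucose monitoring during the" β-OH-B infusion. The stated aim is early detection of hypoglycaemia.

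**Monitoring for everyone.** The same section says: "Blood glucose and electrolytes are monitored throughout the study with the instantaneous-result device". It gives no interval. The safety row of Table 1, repeated in Table 2, reads: "Blood safety monitoring before (3 samples) and after (3 samples) the infusion: glucose, potassium with iSTAT".

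**Duration.** "Each group will receive a 6-hour (3-hour in group III) prime-continuous infusion of racemic" β-OH-B. The paragraph on the NaHCO3 control infusion carries the same glucose monitoring over to those days.

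**Other safeguards.** To lower the chance of hypoglycaemia, "subjects will be asked to withhold their antidiabetic therapy on the day of the studies", until a meal at the end. There is also a symptom trigger: "If at any time a subject develops any symptoms suggestive of hypoglycemia", glucose is measured at once. Treatment with carbohydrate and a 15-minute recheck follow if hypoglycaemia is found.

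**The concern.** The rule is meant to pick out subjects at risk of hypoglycaemia from their diabetes treatment. It names secretagogues and omits insulin, the other permitted treatment that can itself cause hypoglycaemia. As written, a subject on insulin alone, or on insulin plus metformin, with no past sulfonylurea use falls into the class the protocol calls unlikely to become hypoglycaemic.

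What is at stake is participant safety. These are fasting patients with NYHA Class II-III heart failure, infused for 3 to 6 hours, with the only stated meal at the end of the day. Eligibility starts at an HbA1c of 5.5%, so well-controlled insulin users can enrol. The endpoint, the analysis and the sample size are not affected.

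**Working it through.** The protocol gives no figure to reproduce here. The check sets the eligibility text against the monitoring text and then counts scheduled readings.

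**Who is covered by the hourly rule**

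| Permitted treatment | Hourly glucose stated? |
|---|---|
| Sulfonylurea, alone or in combination | Yes |
| Insulin plus sulfonylurea | Yes |
| Insulin (with or without metformin), past sulfonylurea use | Yes, through history |
| Insulin (with or without metformin), no secretagogue history | **No** |
| Diet/exercise or metformin only, no secretagogue history | No (consistent with the premise) |

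**What the uncovered insulin user has on an MRI day**

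- Scheduled glucose before the infusion: 3 samples (Tables 1 and 2).
- Scheduled glucose at the end: 3 samples. The Study Protocol section times the repeat bloods at 360, 365 and 370 minutes, or at 180, 185 and 190 minutes in Group III.
- In between: general monitoring with no interval. The draws every 30 to 60 minutes on MRI days are specified for β-OH-B and acetoacetate, not for glucose.

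No checking interval is therefore stated for up to about 6 hours (3 hours in Group III).

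**What a subject with a secretagogue history has in addition.** Counting hourly readings strictly inside the infusion:

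- 6 hours (Groups I and II): 60, 120, 180, 240 and 300 minutes = 5 readings.
- 3 hours (Group III): 60 and 120 minutes = 2 readings.
- Group II has two 6-hour MRI-day infusions (β-OH-B and NaHCO3): 2 × 5 = 10 readings, taking the NaHCO3 day to be monitored in the same way.

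**Can the general monitoring phrase be read as hourly?** Not easily. If it already meant hourly for all, the separate rule for secretagogue users would add nothing.

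**PET days (Group II only).** The Myocardial Glucose Uptake section plans blood draws about every 30 to 60 minutes during the infusion, and the PET panel in Table 2 includes glucose. The samples exist, although the text does not say that glucose is read in real time.

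**The case against.** The strongest reply is that monitoring is not absent. Point-of-care glucose throughout the study applies to every subject, insulin users included, and only the interval is missing. The silence of Tables 1 and 2 is weak evidence, because their safety rows also omit the hourly sulfonylurea checks that the text plainly requires.

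There are further layers of protection. High-dose insulin is excluded, antidiabetic drugs are withheld that day, and three glucose readings precede the infusion. Symptoms prompt an immediate test, and staff are drawing blood every 30 to 60 minutes anyway. The rule turns on history rather than current use, so it already captures insulin users who once took a sulfonylurea. The remaining group may be small or even empty. The premise sentence also contains a stray character, so it should not carry the argument alone.

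Much of this stands. It is right that monitoring exists, that the tables are not an exhaustive list, that the affected number is unknown, and that 5 (or 2) additional readings is an upper bound. The hourly rule itself is intact, however, and it names only secretagogues.

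The safeguards do not justify the difference in treatment. Withholding, pre-infusion samples, the symptom trigger and general monitoring all apply equally to sulfonylurea users, and the protocol still judged hourly checks necessary for them. Withholding covers the study day only, and insulin taken the evening before is not addressed. Waiting for symptoms is not the early detection that the rule sets out to provide.

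**Conclusion.** The concern holds. The plan states a safety rule whose scope does not match its own eligibility criteria: insulin users with no secretagogue history get a weaker stated schedule than sulfonylurea users, and no reason is given.

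On MRI days the difference is about 5 stated interim readings against no stated number in a 6-hour infusion, 2 against no stated number in a 3-hour infusion, and about 10 over Group II's two MRI days. These counts measure scheduled checks, not risk. The documents give neither the share of subjects on insulin without a secretagogue nor a hypoglycaemia rate for low-dose insulin withheld that day.

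The conclusion rests on reading the general monitoring phrase as setting no interval, and on the NaHCO3 days following the same rules as the β-OH-B days. It is a change that should be made. It is inexpensive and concerns safety only.

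**What to change.** **Wording.** In the Study Protocol section, name insulin in the premise and extend the rule. Suggested text: *Subjects treated with insulin, or with a history of taking an insulin secretagogue, will have iSTAT glucose measured hourly during every infusion, whether β-OH-B or NaHCO3.*

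**Supporting details**

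- The repeat MRI starts after 5 hours (2 hours in Group III), so take that hour's reading before the subject enters the scanner.
- On PET days, read glucose on the iSTAT at the draws already planned.
- Add the interim checks to the safety rows of Tables 1 and 2, for sulfonylurea users as well.

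The first change is the essential one; the others make it workable and visible to site staff.

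**Cost.** Up to 5 additional point-of-care readings per 6-hour infusion and up to 2 per 3-hour infusion for each affected subject; fewer if the general monitoring already supplies some. The device and catheters are in place, and blood is already drawn every 30 to 60 minutes for β-OH-B, so no extra venepuncture is needed. The downside is a few cartridges, some staff time and a protocol amendment.

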**Table 2. Events for subjects in GROUP II:**

Visit Assessments Schedule	Visit 1 Screening DAY -30 to -7	Visit 2 MRI Study 1 Day 0-30	Visit 3 MRI Study 2 Day 7-30 after MRI Study 1	Visit 4 PET Study 1 Day 7-30 after MRI Study 2	Visit 5 PET Study 2 Day 7-30 after PET Study 1
Routine Blood Chemistrys, CBC, UA, lipid profile, TSH/T4, A1c, NT-proBNP, hCG	X				
ECG, DXA, ECHO (if not done within 3-6 months of screening)	X				
POC urine pregnancy test				X	X
Vital signs	X	X	X	X	X
Baseline Cardiac MRI and baseline blood samples $\times$ 3: $\beta$ -OH-butyrate, acetoacetate, glucose, FFA, lactate, pyruvate, glycerol, HCO 3 , insulin/C-pep, glucagon, renin and aldosterone		X	X		
Blood safety monitoring before (3 samples) and after (3 samples) the infusion: glucose, potassium with iSTAT		X	X	X	X
6-hour prime-continuous infusion of $\beta$ -OH-B (0.8 M solution; pH adjusted to 7.24) to increase the plasma $\beta$ -OH-		X		X	
6-hour prime-continuous infusion of NaHCO 3 (0.12 M solution); volume to be infused will be the same as $\beta$ -			X		X
Post-infusion Cardiac MRI and blood samples $\times$ 3: NT-proBNP, $\beta$ -OH-butyrate, acetoacetate, glucose, FFA, lactate, pyruvate, glycerol, HCO 3 , insulin/C-pep,		X	X		

18F-2-DOG/15O-H 2 O PET study and blood samples x 12: NT-proBNP, $\beta$ -OH-butyrate, acetoacetate, glucose, FFA, lactate, pyruvate, glycerol, HCO 3 and hematocrit (with iSTAT), insulin/C-pep and glucagon, erythropoietin, urine 18F-radioactivity.				X	X
---	--	--	--	---	---

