Currently, it is not known what plasma  $\beta$ -OH-B level is required to observe an improvement in LV diastolic/systolic function. Based upon the study of Gormesen et al (70), we anticipate that an increase in plasma  $\beta$ -OH-B of ~2 mmol/L will be adequate to augment myocardial  $\beta$ -OH-B uptake sufficiently to switch the myocardium from glucose to ketone utilization and result in an improvement in cardiac function. Therefore, subjects in GROUP II will be studied on two occasions with NaHCO3 infusion to serve as time controls. Since we previously have shown that Na- The total volume of  $\beta$ -OH-B and NaHCO3 to be infused will be the same to obviate any effect of volume on cardiac function. Blood glucose and electrolytes will be monitored similarly as described above for  $\beta$ -OH-B infusion. As mentioned above, the volume will not exceed 300 ml to avoid volume overload. We are unaware of any evidence that the NaHCO3 infusion has any effect on cardiac function. We have not included a time control study for the low and high dose B-OH-B infusion studies although, depending

upon the results with the lower and higher B-OH-B infusions, we may choose to perform the control NaHCO3 infusion in these groups as well.

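### The Group II bicarbonate control matches the ketone infusion on time and volume but carries about one-seventh of its solute, so on its own it cannot attribute an LV change to ketones

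*Combined protocol and SAP*

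**What the plan says.** Group II is the only group with a planned control. Its participants have one ketone and one NaHCO3 session for MRI, and the same pair for PET. The Study Protocol section calls the NaHCO3 sessions time controls and adds that the total volume of the two solutions "to be infused will be the same to obviate any effect of volume on cardiac function". It also states that "the volume will not exceed 300 ml to avoid volume overload", and that the authors know of no cardiac effect of NaHCO3.

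The strengths are given in two places:

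- Table 2, ketone: "0.8 M solution; pH adjusted to 7.24"
- Table 2, control: "0.12 M solution); volume to be infused will be the same as" the ketone solution (the rest of the cell is lost)
- Study Protocol, ketone: "100 mg/mL solution; pH adjusted to 7.4"

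The Group II rate is "Prime = 1.5 mg/kg.min for 20 minutes and constant rate = 0.75 mg/kg.min until study end". The repeat MRI comes after 5 hours of infusion, or 2 hours in Group III. Groups I and III have no planned NaHCO3 session, although one may be added later. The surviving text does not discuss sodium or osmotic load. The Expected Results section would take an improvement in LV function at the two higher ketone levels as support for the ketone hypothesis.

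**The concern.** The plan treats volume as a confounder worth removing, and removes it by equalising the volume in the bag. The two solutions differ several-fold in solute. If the ketone solution is a sodium salt it is strongly hypertonic, and such a solution draws water into the extracellular and plasma space. The same number of millilitres then need not mean the same effect on cardiac loading.

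Participants have NYHA Class II-III heart failure and an ejection fraction below 45%. Stroke volume, diastolic volume, peak filling rate and E/A ratio all depend on loading. A difference in LV function between the two sessions could come from the ketone, from the extra solute, or from both. The plan has no other controlled contrast to tell these apart, and its conclusion about the ketone hypothesis depends on doing so.

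**Working it through.** **Inputs.** Strengths from Table 2 and the Study Protocol section; infusion rates and MRI timing from the Study Protocol section. Molecular weights follow from the chemical formulas: 126.09 for the sodium salt and 104.10 for the free acid. Body weight is an assumption, 60 to 100 kg, because the documents give only BMI limits.

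**1. Reproduce the stated ketone strength.**

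- As sodium salt: 100 mg/mL / 126.09 = 0.793 M, within 1% of the 0.8 M in Table 2.
- As free acid: 100 / 104.10 = 0.961 M, which does not match.

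The two stated strengths agree only for the sodium salt. The near-neutral pH also needs a counter-cation. This is a strong inference, not a statement in the plan.

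**2. Solute ratio at equal volume.**

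| Ketone strength | Ketone / control | Control as a fraction |
|---|---|---|
| 0.8 M (Table 2) | 0.8 / 0.12 = 6.7 | 0.150 |
| 0.793 M (100 mg/mL, sodium salt) | 6.6 | 0.151 |
| 0.961 M (100 mg/mL, free acid, neutralised) | 8.0 | 0.125 |

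With two particles per formula unit (ideal dissociation), nominal osmolarity is 2 x 0.8 = 1.6 Osm/L, or about 1,600 mOsm/L, against 2 x 0.12 = 0.24 Osm/L, or 240 mOsm/L.

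**3. Amount delivered by the start of the Group II repeat MRI (300 min).**

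- Dose: 1.5 x 20 + 0.75 x 280 = 240 mg/kg.
- Volume: 240 / 100 = 2.4 mL/kg in each session, or 144 to 240 mL at 60 to 100 kg, inside the 300 mL limit.
- Cation: 2.4 x 0.8 = 1.92 mmol/kg (ketone) against 2.4 x 0.12 = 0.288 mmol/kg (control).
- Gap: 1.92 - 0.288 = 1.632 mmol/kg.

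| Assumed weight | Volume, each session | Ketone session, mmol Na | Control session, mmol Na | Gap |
|---|---|---|---|---|
| 60 kg | 144 mL | 115 | 17 | 98 |
| 80 kg | 192 mL | 154 | 23 | 131 |
| 100 kg | 240 mL | 192 | 29 | 163 |

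The sodium columns assume the sodium salt. The ratios in step 2 do not depend on which cation is used.

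**4. Can the dose groups separate ketone from solute?** At the start of the repeat MRI, with the 0.8 M solution:

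| Group | Target rise, mmol/L | Dose, mg/kg | Volume, mL/kg | Cation, mmol/kg |
|---|---|---|---|---|
| I (300 min) | 0.5 | 0.4 x 20 + 0.2 x 280 = 64 | 0.64 | 0.51 |
| II (300 min) | 2.0 | 240 | 2.4 | 1.92 |
| III (120 min) | 5.0 | 4.0 x 20 + 2.0 x 100 = 280 | 2.8 | 2.24 |

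From Group I to II, solute and ketone target rise together. From II to III, cumulative solute rises by 2.24 / 1.92 = 1.17 while the ketone target rises 2.5-fold. That step separates the two in part, but Group III receives its load in 2 hours instead of 5, the comparison is between different people, and Group III has no planned control. By the end of infusion (360 and 180 min, rates as written) the doses are 285 and 400 mg/kg, a ratio of 1.40.

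**The case against.** The plan describes these sessions as time controls with equal infused volume, and it delivers both. It never promises to match sodium or osmotic load. That stands: a reader might infer that the control fails its purpose or is useless, and the documents do not support this. It is incomplete in one respect.

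The salt form is not stated, and the text is damaged where a rationale might have been: a sentence about a sodium compound breaks off just before the volume-matching sentence. This also stands. Silence on sodium cannot be called an omission from the plan, and the mmol figures are conditional. The 0.8 M and 0.12 M strengths and the equal-volume rule are intact and do not depend on the missing words.

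The documents give no estimate of what an extra 98 to 163 mmol of sodium over 5 hours does to EF. A reader might infer that the extra sodium would produce a false benefit, or hide a true one. Neither the direction nor the size is established. The point needs only that the two influences are not separated.

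Differential volume expansion would be partly visible in data already planned: MRI diastolic volume, renin, aldosterone, HCO3, electrolytes and vital signs. That is a real mitigation, but the Statistical Analysis section assigns these measurements no role as a check or adjustment.

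Finally, the loading argument concerns LV function. A reader might extend it to the PET glucose-uptake contrast, which uses the same two solutions. The argument does not by itself undermine that contrast.

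**Conclusion.** The point holds as a limit on interpretation and should be fixed. At equal volume the control carries about 1/6.7 of the ketone session's solute (1/6.6 to 1/8.0, depending on how the ketone strength is read). If the ketone is the sodium salt and participants weigh 60 to 100 kg, the gap at the start of the repeat MRI is about 98 to 163 mmol of sodium. The aim of removing any volume effect is only partly met: infused volume is equal, but the effect of that volume on cardiac loading need not be. The Group II contrast cannot by itself attribute an LV change to ketones, and the dose groups help only in part.

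**What to change.** - State the salt form of the ketone infusate, and reconcile the two strengths in Table 2 with the aim of removing any volume effect given in the Study Protocol section. Composition and its safety are for the sponsor and the pharmacy; no solution is proposed here.
- If the solutions stay as they are, describe the LV contrast in the Study Protocol and Expected Results sections as ketone solution versus a control matched on time and volume but lower in solute. Do not attribute an LV change to ketones alone.
- In either case, tabulate sodium (or cation) and volume delivered per kg for each session and dose group beside the EF change.
- Report diastolic volume, renin, aldosterone, HCO3 and electrolytes by session as checks on differential volume expansion. All are already collected.

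The wording and reporting changes cost a narrower conclusion and a little more analysis, with no added visits or participants. Any change to a solution would be a separate decision with its own safety review.

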At time zero a prime-continuous infusion of  $\beta$ -OH-B (prime = 1.5 mg/kg.min for 20 minutes; continuous infusion = 0.75 mg/kg.min) is started and continued for 380 minutes, and blood samples are drawn approximately every 30 to 60 minutes during the infusion. At 250 minutes to the start of the  $\beta$ -OH-B infusion, a 20-minute transmission scan is performed followed by a repeat cardiac O-water-PET study. At 300 minutes [F]fluoro-2-deoxy-D-glucose (185 MBq) is injected and a dynamic PET scan is performed for measurement of myocardial glucose uptake as previously described (19,78,79). At 360 minutes to the start of the  $\beta$ -OH-B infusion, two consecutive 20-minute dynamic scans of the abdominal and thigh area are performed to measure kidney and skeletal muscle glucose uptake. Urine will be collected before and after the 18F-FDG-PET scan to calculate endogenous glucose production (80). In ~14-30 days subjects will return for a repeat 18F-FDG-PET study with one exception: NaHCO3 will be infused instead of  $\beta$ -OH-B. The two studies will be performed in random order. All radioactive tracers are produced at the on-site cyclotron radiochemistry facility in the RadiolImaging Institute (RII) at the UTHSCSA.

For subjects in Group II, cardiac MRI studies (two study days, one with  $\beta$ -OH-B and other with NaHCO3 infusion) are performed before PET studies. Depending on the scanner availability, however, we may choose to perform PET studies before the cardiac MRI studies.

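### Group II's per-kg infusion rates exceed the stated 300 mL maximum in eligible patients above 100 kg on PET days and above about 103-105 kg on MRI days

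*Combined protocol and SAP*

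**What the plan says.** All references are to the combined protocol and SAP.

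- **Volume limit.** Study Protocol, in the paragraph on the Group II NaHCO3 time control: "As mentioned above, the volume will not exceed 300 ml to avoid volume overload". No weight is attached to the figure, and no earlier statement of it appears in the text available.
- **Dose.** Study Protocol: "GROUP II: Prime = 1.5 mg/kg.min for 20 minutes and constant rate = 0.75 mg/kg.min until study end". The solution is described as "100 mg/mL solution; pH adjusted to 7.4". Tables 1 and 2 describe it as 0.8 M.
- **Duration on MRI days.** Study Protocol: "Each group will receive a 6-hour (3-hour in group III) prime-continuous infusion of racemic" β-OH-B. The final blood samples come slightly later: "the cardiac MRI will be repeated. All baseline blood samples will be repeated at 360, 365, and 370 minutes (6 hours) or at 180, 185". The rate runs to the end of the study, so 370 min is the upper reading.
- **Duration on PET days.** Myocardial Glucose Uptake section: "continuous infusion = 0.75 mg/kg.min) is started and continued for 380 minutes". This is consistent with the last imaging, which starts at 360 min, when "two consecutive 20-minute dynamic scans of the abdominal and thigh area are performed". Table 2 labels the same infusion as 6 hours.
- **Control days.** Table 2 gives the NaHCO3 infusion on Visits 3 and 5, with the "volume to be infused will be the same as" that of β-OH-B.
- **Body size.** The Subjects paragraph admits BMI 23-38 kg/m² and sets no upper limit on weight.

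**The concern.** The dose scales with weight and the volume limit does not. At one solution strength, some weight must exist above which the stated rate, duration and limit cannot all be met. The question is whether eligible patients reach it.

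The limit protects NYHA Class II-III patients with reduced ejection fraction from fluid overload. For a patient above the threshold, either the limit is exceeded or the patient receives less than the stated per-kg dose or duration. The second outcome also matters statistically. The study aims to relate the rise in β-OH-B to cardiac function, and the Statistical Analysis section compares EF changes across the three infusion groups. It has no visible rule for a patient who received less than the group's dose because of body weight.

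**Working it through.** **The plan's own figure.** No derivation is given for 300 mL, so there is nothing to reproduce. The Group II PET infusion gives exactly 300 mL at 100 kg, but that this is where the figure came from would be a guess.

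**Formula.** Volume per kg = [prime rate × 20 + constant rate × (T − 20)] / concentration. Threshold weight = 300 / (volume per kg). Inputs are 1.5 and 0.75 mg/kg/min, 100 mg/mL, and T = 360, 370 or 380 min.

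| Session | mg/kg | mL/kg | 300 mL reached at |
|---|---|---|---|
| MRI, 360 min | 30 + 0.75 × 340 = 285 | 2.85 | 300/2.85 = 105.3 kg |
| MRI, 370 min | 30 + 0.75 × 350 = 292.5 | 2.925 | 300/2.925 = 102.6 kg |
| PET, 380 min | 30 + 0.75 × 360 = 300 | 3.00 | 300/3.00 = 100.0 kg |

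If PET days follow Table 2's 6-hour label, the first row applies to them too (105.3 kg).

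**Are these weights eligible?** The documents give no weights or heights, so heights of 1.60, 1.70 and 1.80 m are assumed. Weight at BMI 38 is 38 × height².

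| Height | Weight at BMI 38 | MRI 360 min | MRI 370 min | PET 380 min | Excess over 300 mL |
|---|---|---|---|---|---|
| 1.60 m | 97.3 kg | 277 mL | 285 mL | 292 mL | none |
| 1.70 m | 109.8 kg | 313 mL | 321 mL | 329 mL | 4-10% |
| 1.80 m | 123.1 kg | 351 mL | 360 mL | 369 mL | 17-23% |

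The BMI at which the limit is reached is threshold weight / height². At 1.70 m it is 36.4, 35.5 and 34.6 for the three sessions; at 1.80 m it is 32.5, 31.7 and 30.9. All lie inside 23-38. The shortest eligible patient who can be affected is √(threshold/38) tall: 1.66, 1.64 and 1.62 m respectively.

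**Sensitivity to the solution strength.** The tables' 0.8 M needs a molar mass that the documents do not give. Read as the sodium salt (assumed, about 100.9 mg/mL), the thresholds are 300/(300/100.9) = 100.9 kg for PET and 103.5-106.2 kg for MRI, almost unchanged.

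**Sensitivity to the prime.** If the constant infusion ran alongside the prime instead of following it, the thresholds fall to 95.2 kg (PET) and 97.6-100.0 kg (MRI). No variant tried removes the conflict.

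**The case against.** **A handling rule may have been lost.** The NaHCO3 paragraph contains a sentence that breaks off partway, and the limit refers back to a statement that is not in the available text. A reader might infer that the sponsor never decided what to do above the threshold; the documents do not support that. What stands is narrower: the visible rates, durations and limit conflict.

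**The limit may simply override the rates.** This is a fair reading. Even so, the stated per-kg dose or duration is then not delivered, and the visible text does not say which is reduced.

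**The effect is small.** This stands. Only larger patients are affected, and Group II has 19 patients (Study Protocol) or 26 (Sample Size). NaHCO3 volume is matched to β-OH-B volume, so the within-patient control comparison stays balanced for volume. β-OH-B is sampled every 30-60 min, so a shortfall in exposure would probably be visible.

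**A mid-scan stop is a tempting but weak inference.** If the infusion were cut off at 300 mL, it would end at 20 + (300/W − 0.3)/0.0075 min: about 344 min at 110 kg and 305 min at 123.1 kg. The repeat MRI and the FDG injection both come at 300 min, so a reader might conclude that scans would run without infusion. Volume is known from weight beforehand, so lowering the rate in advance is the more likely response. Nothing in the plan says the infusion would be stopped.

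**Group III.** At its rates the same limit would be passed above 300/4.00 = 75.0 kg (180 min) or 300/4.20 = 71.4 kg (190 min). A reader might infer a larger breach there. The limit sits in the Group II control paragraph, and no text extends it to Group III.

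**Conclusion.** The point holds for Group II. Above 100 kg on PET days and about 103-105 kg on MRI days, the stated rate, duration and 300 mL maximum cannot all be met, and the BMI criterion admits such patients. The NaHCO3 days follow because their volume is matched.

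The size is modest: no excess at 1.60 m, about 4-10% at 1.70 m and 17-23% at 1.80 m, all at the maximum BMI of 38. How many patients are affected cannot be said, because the documents give no weight distribution. The result assumes 100 mg/mL, a prime that precedes the constant rate, and the illustrative heights.

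Reading 0.8 M as free acid (molar mass again assumed, about 83.3 mg/mL) would lower the thresholds to about 83 kg (PET) and 85-88 kg (MRI). The documents do not establish that reading, so the larger problem it implies is not claimed. Nor is any error claimed for Group III, only that the scope of the limit should be stated. The correction should be made because the limit is a safety statement and the remedy is cheap.

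**What to change.** 1. **Preferred: cap the dosing weight.** Use one maximum dosing weight of 100 kg for every Group II β-OH-B and NaHCO3 infusion, on MRI and PET days alike. The largest volumes are then 285 mL (360 min), 292.5 mL (370 min) and 300 mL (380 min). The cost is a lower per-kg dose in heavier patients: 100/110 = 91% at 110 kg and 100/123.1 = 81% at 123 kg. Record the delivered volume, flag capped patients in the dose-response analysis, and interpret them using the β-OH-B levels already measured.
2. **Alternative: restate the maximum.** After a safety check, replace 300 mL with a limit that matches the rates, about 3.0 mL/kg. This keeps the per-kg dose but allows about 369 mL at 123.1 kg. A stronger solution for heavier patients would also keep the dose, but nothing in the documents supports its use, so it is not recommended here.
3. **Under either option,** state when the MRI-day infusion ends (360 or 370 min), whether PET days run 360 or 380 min, and whether the limit covers Group III. If it does, Group III needs its own rule, since 100 kg × 4.0-4.2 mL/kg is 400-420 mL.

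The cost is a short protocol clarification and one recorded field, plus a safety check under option 2. No extra patients, visits or procedures are needed.
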